**Important Instructions for Using This Protocol Template:**

This template is provided to help investigators prepare a protocol that includes the necessary information needed by the IRB to determine whether a study meets all applicable criteria for approval.

**1. GENERAL INSTRUCTIONS:**

- Prior to completing this protocol, ensure that you are using the most recent version by verifying the protocol template version date in the footer of this document with the current version provided in the CATS IRB Library.
- Do not change the protocol template version date located in the footer of this document.
- Some of the items may not be applicable to all types of research. If an item is not applicable, please indicate as such or skip question(s) if indicated in any of the instructional text.
- **GRAY INSTRUCTIONAL BOXES:** Type your protocol responses below the gray instructional boxes of guidance language. If the section or item is not applicable, indicate not applicable.
  - **Do NOT delete the instructional boxes from the final version of the protocol.**
- Add the completed protocol template to your study in CATS IRB (<http://irb.psu.edu>) on the “Basic Information” page.

**2. CATS IRB LIBRARY:**

- Documents referenced in this protocol template (e.g. SOP's, Worksheets, Checklists, and Templates) can be accessed by clicking the Library link in CATS IRB (<http://irb.psu.edu>).

**3. PROTOCOL REVISIONS:**

- When making revisions to this protocol as requested by the IRB, please follow the instructions outlined in the guides available in the Help Center in CATS IRB (<http://irb.psu.edu>) for using track changes.

- Update the Version Date on page 1 each time this document is submitted to the IRB office with revisions.

**If you need help...**

Aim 3: Analyze Aevidum's impact on school mental health referrals and school climate indicators through faculty interviews. Hypothesis: School staff interviews will allow for a richer understanding of the challenges and successes with Aevidum curriculum and club activities that cannot be captured through student surveys, but will be crucial in planning for larger scale program evaluation.

Students from all 10 participating schools in grades 9-12th will be asked to complete a pre-post survey using the University of Michigan Depression Center (UMDC) Peer-to-Peer Depression Awareness Assessment to address aims 1 and 2. Separate interviews will be conducted via ZOOM with up to 5 school staff member from each school (n=50) to supplement the UMDC survey results for more in-depth information on school climate and student mental health referrals.

### 1.2 Primary Study Endpoints

State the primary endpoints to be measured in the study.

Clinical trials typically have a primary objective or endpoint. Additional objectives and endpoints are secondary. The endpoints (or outcomes), determined for each study subject, are the quantitative measurements required by the objectives. Measuring the selected endpoints is the goal of a trial (examples: response rate and survival).

The primary endpoints are significant improvements in knowledge and help-seeking behaviors between pre- and post-survey measures using the UMDC Peer-to-Peer Depression Awareness Assessment.

### **1.3 Secondary Study Endpoints**

State the secondary endpoints to be measured in the study.

The secondary endpoints will be 1) improvements in school climate and 2) a greater number of mental health referrals based on qualitative (interviews) with from school staff.

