### 3.3 Early Withdrawal of Subjects

#### 3.3.1 Criteria for removal from study

Insert subject withdrawal criteria (e.g., safety reasons, failure of subject to adhere to protocol requirements, subject consent withdrawal, disease progression, etc.).

The intervention (Aevidum curriculum plus/minus club) will happen regardless of the research. These materials are already freely available and being utilized in schools across the Commonwealth. The research pieces are the student pre-post questionnaires and staff interviews to assess knowledge change, help-seeking and school culture/climate. student participants whose parents did not opt-them out may voluntarily withdraw from the study at any time by declining to have their child complete the pre and post survey.

School staff that participate in interviews at the end of the school year may also decline to answer any demographic questions or interview questions that they do not feel comfortable answering.

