### School Staff Semi-structured Interviews

Zoom interviews (maximum of 50) will be conducted with two school staff members from each school to measure Aevidum's impact on school mental health referrals and school climate indicators. School staff members will be identified by the school contact and invited to participate. Participants will be instructed to turn off their camera and the interview will be recorded (only voices) via PSH HIPAA Compliant Zoom. Interviews will begin with introductions and information on the project. Participants will have the opportunity to ask questions about the study. See School Staff Demographics and Interview Guide to view open-ended questions to address study aims.

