#### **School Staff Semi-structured Interviews**

Semi-structured interviews will also be conducted with up to 5 school staff members at the end of the school year. The main point of contact at the school will identify interested subjects who will be provided a link to review the Summary Explanation of Research, determine eligibility and indicate assent by completion of the demographic survey. Eligible school staff will be contacted by the study team to schedule their interview based on their availability. Up to two participants may be interviewed at the same time. Prior to the Zoom interviews participants will be reminded that their completion in the interview implies their voluntary consent to participate in the research.

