#### School Staff Semi-structured Interviews

Interviews will be analyzed to determine themes and Aavidum curriculum/club impact (Aim 3). Guided by [name] qualitative analysis expertise, thematic categories will be developed by reading and coding themes from the interview transcripts. Themes will be compared and contrasted to illustrate impacts of Aavidum on the selected high schools.

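### The referral endpoint in Section 1.3 claims a greater number, but the plan describes only one end-of-year round of qualitative staff interviews, with no count, baseline or numerical comparison

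*Combined protocol and SAP*

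**What the plan says.** Section 1.3 lists two secondary endpoints: better school climate, and "a greater number of mental health referrals based on qualitative (interviews" with school staff). Aim 3 in Section 1.1 is to "Analyze Aevidum's impact on school mental health referrals and school climate indicators through faculty interviews". The hypothesis under that aim is softer: interviews will give a fuller picture than surveys can and will help plan a larger evaluation.

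On timing, Section 7.2.1 states: "Semi-structured interviews will also be conducted with up to 5 school staff members at the end of the school year". Section 3.3.1 agrees, referring to "School staff that participate in interviews at the end of the school year". Section 5.2.1 sets a minimum of two and a maximum of five staff per school.

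On content, Section 7.2 says that the interviews serve to measure the programme's impact on referrals and climate, and refers to an attachment: "See School Staff Demographics and Interview Guide to view open-ended questions to address study aims".

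On analysis, Section 8.3 says that "thematic categories will be developed by reading and coding themes from the interview transcripts", after which themes are compared and contrasted. Section 7.2 adds a codebook and an inter-rater check on a fifth of the transcripts.

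**The concern.** The endpoint is numerical in its claim and qualitative in its method. Coding transcripts by theme can show that staff believed referrals had changed, and how and why. It cannot show that the number was greater, because it yields no number to set beside another.

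The stake is what the trial may conclude. Section 2.3 says that the results are meant to build an evidence base for the programme and to support its future funding, and Section 11.2 names improved referrals as a potential benefit to schools. A report that listed this endpoint as met would carry a quantitative statement into that use. The support would be the recollection of staff whom the school contact put forward (Sections 7.2 and 7.2.1). All schools deliver the curriculum (Section 3.1), so no untreated school exists against which to judge such an impression.

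**Working it through.** The plan gives no figure to reproduce for this endpoint: no baseline referral rate, effect size or power, and Section 8.2 marks the interview sample size as not applicable. The check is therefore a comparison of what the endpoint needs with what the sections describe.

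**1. What the endpoint needs.** A greater number requires at least two counts on the same definition: an earlier and a later period in the same schools, or one arm and the other.

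**2. Data sources described.** Section 3.3.1 states: "The research pieces are the student pre-post questionnaires and staff interviews to assess knowledge change, help-seeking and school culture/climate". A brief educator feedback survey is also planned, but Section 4.1 describes it as a survey on the training. No section describes extraction of referral logs, school records or school-level totals.

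**3. Time points.** The student survey has two: September-October 2021 (Section 7.2.1) and April-May 2022 (Section 7.2.2). The interviews have one, at the end of the year. No start-of-year interview or prior-year referral figure is described.

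**4. Volume of interview data.** At 2 to 5 staff in each of 10 schools, the range is 10 × 2 = 20 to 10 × 5 = 50 interviewees, the upper end matching the stated maximum of 50. This is one round of many interviews, not a single interview. It is still up to five accounts per school, with no rule for turning them into a school total.

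**5. Analysis.** The mixed models in Section 8.3 apply to survey items collected at each time point. The group-by-time comparison covers knowledge, help-seeking, school environment/stigma and program visibility. Referrals appear in neither. The interview analysis is thematic, with no count, rate, estimate or interval.

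**6. Tally for referrals.**

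| Element | Needed | Described |
|---|---|---|
| Counts | at least 2 | 0 |
| Baseline or comparator figure | 1 | 0 |
| Numerical comparison, over time or by arm | 1 | 0 |
| Qualitative account from staff | not sufficient | yes, one round |

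**7. The same check for school climate.** The result differs. Aim 2 in Section 1.1 places school environment/stigma on the UMDC assessment. Section 5.6.3.2 says that the tool covers culture and climate change. Section 8.3 models its items before and after and compares the arms on them. Section 1.1 presents the interviews as a supplement to that survey. Climate therefore has a quantitative measure; what Section 1.3 lacks is a statement of which source defines the endpoint.

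**The case against.** The strongest defence is that the endpoint openly calls itself qualitative, that the Aim 3 hypothesis promises only a richer understanding, and that no test is planned, so nobody is committed to reporting a rise. This stands in part: the design suits the hypothesis, and an unsupported report is a risk rather than a certainty. It does not remove the mismatch, because Section 1.3 still defines success as a greater number and Section 7.2 still says that the interviews measure impact.

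A second defence is that the interview guide is an attachment, and that the protocol template tells authors to leave actual questions out. A question about referral numbers cannot be ruled out. A reader might infer that no count is collected at all; the documents support only that none is described. Figures recalled in an interview would still have no planned baseline and no planned numerical analysis.

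A reader might also infer that the single time point is itself the flaw. It is not: one request at year end could obtain totals for two years. The flaw is that no such totals are described.

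Finally, a reader might extend the criticism to school climate. The documents do not support that, because the student survey measures climate before and after and the arms are compared on it.

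**Conclusion.** The point holds for referrals. As described, the plan can support a statement about change in referrals as staff perceive it, and cannot support a statement that the number was greater: none of the two or more counts required is described. The mismatch touches one secondary endpoint and the related wording in Aim 3 and Section 7.2. It leaves the primary endpoints, the sample size and the survey models unchanged. It deserves correction because it alters what may be concluded, and the correction is cheap.

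The conclusion rests on two assumptions: that the unseen interview guide does not set up a formal count with a comparison period, and that no other attachment provides for school referral records. If either does, the protocol should say so and state the analysis.

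**What to change.** 1. In Section 1.3, replace the referral endpoint with *staff-perceived change in mental health referrals (qualitative)*. Bring the wording of Aim 3 and of the interview paragraph in Section 7.2 into line, and draw no conclusion about a greater number.

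2. Also in Section 1.3, state that school climate is measured by the pre/post UMDC school environment/stigma items, with the interviews as a supplement. Do not relabel climate as qualitative only.

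3. If a count is wanted, ask one designated contact per school for aggregate referral totals and enrolment for 2020-21 and 2021-22, under one stated definition of a referral. Do not place the item on the staff demographic form: each interviewee completes that form, so a school could return up to five conflicting totals. Report the totals descriptively by arm, with enrolment as denominator. Do not credit a within-school rise to the programme: the earlier year falls in the pandemic, to which Section 1.1 refers, and no school goes without the curriculum.

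Items 1 and 2 cost only rewording; the downside is that the endpoint claims less. Item 3 adds a small request to each of the 10 schools and depends on whether schools hold such totals, which the documents do not show.

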## **2.0 Background**

### **2.1 Scientific Background and Gaps**

Describe the scientific background and gaps in current knowledge.

For clinical research studies being conducted at Penn State Health/Penn State College of Medicine, and for other non-PSH locations as applicable, describe the treatment/procedure that is considered standard of care (i.e., indicate how patients would be treated in non-investigational setting); and if applicable, indicate if the study procedure is available to patient without taking part in the study.

It is important for schools to seek out opportunities to expand student's knowledge and awareness of mental health and suicide prevention, since suicide is the second leading cause of death for 10-24 year olds. Schools can be an ideal setting to offer suicide prevention and mental health programming supplemental to state-mandated requirements (e.g., Act 71 mandated curriculum). Prior research revealed that students are not more likely to commit suicide despite increased discussion on the topic, which actually has the potential to decrease distress in students who have suicidal ideation. Most adolescents prefer to talk to peers about suicide and mental well-being, and student-led programming can help to open that conversation. Though parents and other adults who work with youth encourage those at risk to report to trusted adults, a minority actually do. Reasons for this include lack of knowledge, low self-efficacy, the belief that discussing suicide is taboo, and keeping a peer's wish for secrecy. Programming – like Aevidum – can aid in increasing knowledge, awareness and help-seeking behaviors within schools.

Since 1989, PA has conducted the biennial PA Youth Survey (PAYS) for youth in 6th, 8th, 10th and 12th grades to address relevant adolescent risk and protective factors. The 2017 PAYS survey found that 16.0% of PA students had seriously considered attempting suicide. Additionally, female youth are over two times more likely to exhibit suicidal ideation and more likely to make suicidal attempts than male youth, but male youth are more likely to complete. To address these concerns, schools are placing greater value on mental-health and suicide prevention programming. There is an opportunity for schools to positive influence mental health behaviors, since students spend about half of their waking hours in a school setting. In addition to PA Act 71 mandated curriculum, opportunities like Aevidum can aid schools by empowering students to support one another and expand their knowledge about mental health, stigma and help-seeking behaviors.

### **2.2 Previous Data**

Describe any relevant preliminary data.

During the 2015-2016 academic year, a group of researchers from the University of Michigan conducted a school-based study. They enrolled 10 schools in the school-based Peer-2-Peer Depression Awareness Program that aimed to decrease mental illness and promote well-being. Students were trained as peer leaders to design and implement a depression awareness campaign. That group of researchers found increased mental health awareness and literacy among students, and noted that the program may have improved detection of depression and decreased depressive episodes. We are planning to use the same pre-posttest questionnaire in this study to track changes in student's knowledge and help seeking intentions related to mental health following exposure to the Aevidum curriculum (plus/minus club), which is in widespread use in many Pennsylvania schools.

### 2.3 Study Rationale

Provide the scientific rationale for the research.

The proposed intervention targets high schools to improve adolescent knowledge and help seeking regarding mental health. Aevidum was established in 2009 as a student-led initiative to raise awareness and reduce the stigma surrounding mental illness. Their mental health curriculum and club activities are currently used in over 300 schools in PA and surrounding states. In comparison to current interventions, Aevidum is unique in that it provides students the opportunity to build a strong support system among peers. Aevidum's curriculum and club activities provide an opportunity for schools and students to engage with mental health and suicide prevention materials with a student-directed method. Youth voice is a powerful tool that schools and communities can utilize to make mental health and suicide prevention programming more impactful. Allowing youth the chance to lead and let their voices be heard can create greater buy-in for activities. Attitudes, policies and structures change when students are engaged as partners in schools, which can lead to positive change in school culture.

At present, there is not a strong evidence-base for the efficacy of student-led initiatives that aid in reaching mandated Act 71 curriculum standards for mental health and suicide prevention. Aevidum lacks an evidence-base for its curriculum and club programming, which is freely available to schools. To continue offering free resources, while also maintaining and updating these resources to ensure they are innovative and best reflect student needs, Aevidum needs to establish an evidence-base to support future funding. This project plans to evaluate the effectiveness of these efforts in supporting adolescent mental health. Results will be used to inform school-based mental health programming and to establish an evidence-base for the Aevidum program, furthering mental health awareness and education, while also reducing mental health stigma.

## 3.0 Inclusion and Exclusion Criteria

Create a numbered list below in sections 3.1 and 3.2 of criteria subjects must meet to be eligible for study enrollment (e.g., age, gender, diagnosis, etc.).

### Vulnerable Populations:

Indicate specifically whether you will include any of the following vulnerable populations in this research. You MAY NOT include members of these populations as subjects in your research unless you indicate this in your inclusion criteria because specific regulations apply to studies that involve vulnerable populations.

The checklists referenced below outline the determinations to be made by the IRB when reviewing research involving these populations. Review the checklists as these will help to inform your responses throughout the remainder of the protocol.

- **Children** –Review “HRP-416- Checklist - Children”

- **Pregnant Women** – Review “HRP-412- Checklist - Pregnant Women”
- **Cognitively Impaired Adults**- Review “HRP-417- Checklist - Cognitively Impaired Adults”
- **Prisoners**- Review “HRP-415- Checklist - Prisoners”
- **Neonates of uncertain viability or non-viable neonates**- Review “HRP-413- Checklist - Non-Viable Neonates” or “HRP-414- Checklist - Neonates of Uncertain Viability”

[Do not type here]

### 3.1 Inclusion Criteria

Create a numbered list of the inclusion criteria that define who will be included in your final study sample (e.g., age, gender, condition, etc.)

1. Students (grades 9-12) and staff from participating schools. For the first time during the 2021-2022 school year, all participating schools will be implementing the Aevidum curriculum, but only half of the participating schools will implement club activities in addition to the curriculum (n=5 schools will implement just the curriculum, and n=5 schools will implement the curriculum AND club activities).

School staff who participated in the Aevidum Training will be asked to complete a brief survey using our “Educator Training Feedback Survey” (included in supporting documents).

### 3.2 Exclusion Criteria

Create a numbered list of the exclusion criteria that define who will be excluded in your study.

#### Student Pre- and Post- Survey

1. Students not enrolled in one of the participating high schools (n=10)
2. Students not in grades 9-12
3. Students with disabilities that are deemed unable to participate by the school district
4. Non-English speaking students

#### School Staff Semi-structured Interviews

1. Individuals who are non-English speaking
2. Individuals who are <18 years old

### 3.3 Early Withdrawal of Subjects

#### 3.3.1 Criteria for removal from study

Insert subject withdrawal criteria (e.g., safety reasons, failure of subject to adhere to protocol requirements, subject consent withdrawal, disease progression, etc.).

The intervention (Aevidum curriculum plus/minus club) will happen regardless of the research. These materials are already freely available and being utilized in schools across the Commonwealth. The research pieces are the student pre-post questionnaires and staff interviews to assess knowledge change, help-seeking and school culture/climate. student participants whose parents did not opt-them out may voluntarily withdraw from the study at any time by declining to have their child complete the pre and post survey.

School staff that participate in interviews at the end of the school year may also decline to answer any demographic questions or interview questions that they do not feel comfortable answering.

